**C.1.h. Data Analysis:** The primary goal of the R21 phase is to determine the dose response curve to RT for mu suppression and pupillary response. Prior to modeling the form of the curves we will obtain descriptive statistics and graphical summaries for the measures of target engagement on placebo, at each of the active doses. We will also plot the within subject change scores and the overall dose-response curve. To formally determine whether there is target engagement we will fit a logistic dose response curve to the data for each of the outcome measures. We assume that the OT dose response curve can be adequately modeled using a 4-parameter model with a lower asymptote, slope, E50 (point of half of maximum response), and upper asymptote as the parameters. However, we will also fit a 5 parameter model that allows for an asymmetry in the acceleration and deceleration of the change slope to determine whether the additional parameter is necessary to represent the empirical dose response curve. Independent of which of the models for the dose

response curve we finally choose we will determine whether there is target engagement by testing whether the upper asymptote is significantly different from zero using a z-test based on the parameter estimate and its standard error. Specifically this test allows us to determine whether there is a measurable change in the outcome variable of interest at the optimum dose of OT (where the upper asymptote is reached) while borrowing strength across all the measurement points. For the secondary aim, examining the relationship between target engagement and social salience we will use multiple linear regression models with the social salience measures as the outcomes and change in pupillary response and mu suppression in response (OT vs placebo) as the predictors, adjusted for OT dose.

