**Power:** Calculations for the R21 Phase are based on the primary goal of detecting target engagement based on the OT dose response curves for mu suppression and pupillary response using a sample of size  $n=48$ . To estimate power we simulated 10000 replicate data sets following our study design (8 different doses of OT, with 6 observations at each dose) using the effect sizes from our pilot data on pupillary dilation and mu suppression, as well as the results reported in Prehn [31] for 47 normal participants on pupillary dilation, and the results reported in Perry [35] for mu suppression in 24 normal participants.. Specifically, the simulations conservatively assumed that the observed effect sizes represented the upper asymptote (i.e., that the optimal dose had been reached and observations at higher dosage levels than those employed in the respective studies would not show a stronger response). In addition, we assumed that the variances observed at 24, 36, 48, and 60 IU (the middle of the dose range where maximum change in the targets would be expected to occur) were as large as the variances reported in the studies, while the variances at the extreme ends of the range (8, 12, 74 and 84 IU) were half of that. This is based on the patterns of variance heterogeneity common observed for dose response curves.

Under these assumptions the power for detecting a significant upper asymptote is 84% for pupillary response data that show an effect size of  $d = .81$  at the optimal dose, equivalent to the results from our pilot data, and 92% using an effect size of  $d = 1.22$ , the average effect size reported in Prehn [31]. For mu suppression, the power is 89% for an effect size of  $d = 1.03$  at the optimal dose, equivalent to the results in Perry (2010) and 45% for an effect of  $d = .24$ , the average effect seen across task conditions in our pilot data. These are extremely conservative estimates as we expect that these studies were not conducted at the optimal dose, and the estimate of measurement error is most likely inflated as it is based on observations in the steepest part of the dose response curve, where the response is least stable. The wide range of doses that is covered by our design ensures that we will be able to find a stable estimate for the optimal dose of OT.

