**C.1.i. Go/No Go decision: After all 48 subjects have completed the OT challenge, we will evaluate** whether the dose response curves for pupillary response or EEG mu suppression show significant target engagement on OT relative to placebo. If there is a significant departure from placebo on either measure of target engagement, the R33 will be initiated.

**D. Milestones and Timeline:** As noted in the timeline, we anticipate that the start-up for the R21 will be accomplished in 3 months. We view this as feasible since all of the assessments – including the target engagement measures – have already been administered in our group. The 2 month start up of the R33 is also feasible since our group therapists are experienced in social cognition training. The rates of subject recruitment required for the R21 and the R33 are similar to recent studies completed by our group.

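### The power figures are not shown to be conservative across the board, and the 45% for mu suppression was not reproduced from the stated inputs

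*Combined protocol and SAP*

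**What the plan says.** Section C.1.h plans a four-parameter logistic dose-response curve (a five-parameter version is also fitted) and declares target engagement by "testing whether the upper asymptote is significantly different from zero using a z-test based on the parameter estimate and its standard error". The Power paragraph that follows simulates 8 doses with 6 subjects each and gives 84% at d = 0.81 and 92% at d = 1.22 for pupil response, and 89% at d = 1.03 and 45% at d = 0.24 for mu suppression. The last effect size is "the average effect seen across task conditions in our pilot data".

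Two simulation assumptions matter here. First, "the simulations conservatively assumed that the observed effect sizes represented the upper asymptote". Second, the reported variance is kept at 24, 36, 48 and 60 IU, described as "the middle of the dose range where maximum change in the targets would be expected to occur", while "the variances at the extreme ends of the range (8, 12, 74 and 84 IU) were half of that". The support given for the second is: "This is based on the patterns of variance heterogeneity common observed for dose response curves".

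The paragraph then says of all four figures: "These are extremely conservative estimates as we expect that these studies were not conducted at the optimal dose". It adds that measurement error is probably overestimated, because it was observed on the steepest part of the curve.

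Under C.1.i, "If there is a significant departure from placebo on either measure of target engagement, the R33 will be initiated".

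**The concern.** The two assumptions pull in opposite directions. Taking the observed effect as the maximum lowers power. Halving the variance for half the sample raises it, and the two highest doses, which inform the tested upper asymptote most directly, are among those halved. The paragraph counts only the first. Both patient pilots (C.1.e and C.1.f) used 40 IU alone, so they cannot show how variance changes with dose.

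The 45% also looked high beside the other three figures for so small an effect. It matters because d = 0.24 is the only patient estimate for mu suppression and the test feeds the Go/No Go decision. A reader told that 45% is a cautious figure would give a non-significant mu result more weight than the design may support.

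The same sentence names 74 IU, where the opening summary, the Specific Aims and C.1.d list 72 IU.

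**Working it through.** **Inputs from the plan.** 48 completers, 6 at each of 8 doses; a z-test of the upper asymptote in a four-parameter fit; asymptote equal to d; full variance at four doses and half at four.

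**Not stated, so assumed or varied.** Alpha (0.05), sidedness (both tried), E50, slope, lower asymptote (true value 0), handling of singular fits, weighting, and the SD that defines d (the SD of the OT-minus-placebo change at the middle doses, set to 1). The calculations use 72 IU, as in C.1.d; this is not a judgement on which dose is right.

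**1. Can 45% be reproduced at d = 0.24?** Start with a ceiling: all 48 subjects on the plateau and the curve shape known. Two-sided power = Φ(d√I − 1.96).
- Full variance: I = 48; 0.24 × √48 = 1.66; power 38%.
- Halved ends, unweighted: I = 48/0.75 = 64; 0.24 × 8 = 1.92; power 48%.
- Halved ends, weighted: I = 24/1 + 24/0.5 = 72; 0.24 × √72 = 2.04; power 53%.

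So 45% is not impossible, but it lies close to a ceiling that puts even 8 IU on the plateau.

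Next, four-parameter fits with halved ends on 70 curves: E50 24 to 60 IU in steps of 6, with Hill slopes 2 to 8 on log dose or slopes 0.05 to 0.30 per IU. Two-sided asymptotic power is 5-31%. Simulated fits (1000 replicates per setting; weighted and unweighted; singular fits counted as not significant, dropped, or kept) give 5-40% over 70 × 2 × 3 = 420 settings, and none reaches 43%. A second set of fits, which also fixed the lower asymptote at 0, peaked at about 42% of converged fits. The share of singular or failed fits, and the power when they count as not significant, depend on the optimiser; the figures with such fits dropped are steadier.

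**2. What does reach it?** The four-parameter setting closest to all four stated powers has E50 30 IU, slope 0.30 per IU, an unweighted fit and singular fits dropped (6000 replicates):

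| d | Stated | One-sided | Two-sided |
|---|---|---|---|
| 0.24 | 45% | 42.0% | 29.9% |
| 0.81 | 84% | 85.6% | 84.5% |
| 1.03 | 89% | 87.7% | 86.5% |
| 1.22 | 92% | 89.3% | 88.5% |

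With the lower asymptote fixed at 0 (not the planned model), E50 30, Hill slope 8 and converged fits only, one-sided power is 45/87/90/93% and two-sided power at d = 0.24 is 33%.

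A d in raw SDs is another route. With OT-placebo correlation 0.8, the change SD is √(2 × 0.2) = 0.632, so d becomes 0.24/0.632 = 0.379. With known shape and only the 12 subjects at the two top doses on the plateau (I = 12/0.5 = 24), 0.379 × √24 = 1.86, and power is 46%.

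**3. Effect of the halving at d = 0.24.** On the closest curve, two-sided power is 22.0% with full variance and 29.9% with halving, a gain of 7.9 points; one-sided it is 32.5% and 42.0%. On two mid-range curves (E50 38 IU with Hill slope 4.8; E50 42 IU with slope 0.122 per IU) halving adds 4-12 points at d = 0.24, 3.5-8.5 at d = 0.81, and −1 to 5 at d = 1.03 and 1.22.

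**4. Effect of the asymptote assumption.** Share of the maximum reached at 40 IU:
- Mid-range curves: 1/(1 + (38/40)^4.8) = 0.56 and 1/(1 + exp(0.244)) = 0.44. The implied asymptotes are 0.24/0.56 = 0.43 and 0.24/0.44 = 0.55, about 1.8 and 2.3 times the pilot d.
- Closest curve: 1/(1 + exp(−0.30 × 10)) = 0.95. The implied asymptote is 0.24/0.95 = 0.25, so this assumption gives almost no margin.

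**5. The two together.** On the mid-range curves, scaling the asymptote up and restoring full variance raises two-sided power (singular fits dropped) from 21.5% to 37% and from 27% to 52%. As the plan simulated them, with asymptote 0.24 and halved ends, these curves give only about 10-30% two-sided.

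**The case against.** The strongest defence is that the asymptote assumption really is cautious. If 40 IU lies mid-curve, as the plan's own description of the 24-60 IU range suggests, it outweighs the halving (step 5). That stands. A reader might infer from the halving that the powers are overstated on balance; the documents do not support this, because the net direction turns on a curve they do not give. But the mid-range curves that justify the label do not yield 45% two-sided. The curve that comes closest to all four powers puts 40 IU near the plateau, where the label loses its main support. One-sided, the mid-range curves reach 41-43% if singular fits are kept, but keeping them rejects 9-11% of the time two-sided when there is no effect.

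The plan's second reason, overestimated measurement error, partly overlaps the halving. The error is said to be large on the steep part of the curve, where the simulation keeps the reported variance; at the ends it has already been cut by half.

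It is also fair that the problem is missing inputs and not proven false arithmetic. A reader might conclude that 45% is impossible or wrong. It is neither: the ceiling is 48-53%, and a one-sided test or a raw-SD d can produce it.

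Finally, the consequence is limited. The 45% is printed openly and is low by any convention, and Go needs only one of the two measures.

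**Conclusion.** The concern holds in a limited form. The blanket description is unsupported because one assumption that raises power goes unacknowledged: about 4 to 12 points at d = 0.24, and little at d = 1.03 and 1.22. The figures are not shown to be optimistic overall.

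The 45% was not reproduced with a two-sided 0.05 test and d in change-score SDs. Fitted power was mostly 10-35% and at most about 40-42% in any setting tried. It becomes reachable with a one-sided test, exclusion of singular fits in combination with that, or a change SD below the unit of d. None of these is stated, and a test of difference from zero reads as two-sided.

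These results rest on the assumed curves, a true lower asymptote of 0 and the fitting method. They show sensitivity and are not replacement figures. The point should be corrected, but it does not undermine the design.

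**What to change.** 1. Reconcile 74 IU in the Power paragraph with the dose lists in the opening summary, the Specific Aims and C.1.d.
2. Rerun the simulation at the reconciled design doses with the planned four-parameter test, once with halved and once with full reported variance at the end doses, and report both.
3. State alpha, sidedness, E50, slope, lower asymptote, the SD that defines d, any weighting, and how non-converged or singular fits are counted.
4. Restate any of the four powers that the rerun does not confirm, the 45% in particular.
5. Replace the conservative label with a sentence saying that taking the observed effect as the asymptote lowers power and that halving the end-dose variance raises it.

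The cost is a simulation rerun and an edit to one paragraph, possibly with a less favourable figure for mu suppression. Enrolment and procedures do not change.

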## PROTOCOL

### Enhancing Social Cognitive Training with Oxytocin: Linking Target Engagement to Clinical Effects

Intranasal oxytocin (OT) has shown promise as an agent that can effectively improve social processing in disorders that are characterized by impairments in social behaviors, including schizophrenia. However, important gaps in our understanding of OT's effects on the brain have greatly limited its development as a therapeutic agent and made it difficult to interpret mixed research findings. One very important therapeutic function of OT may be its ability to enhance learning of social information. The proposed research will evaluate, in sequential steps, OT's effects on learning social cognitive skills in psychotic patients within a manualized training program that we have developed. The initial step (R21) is to demonstrate target engagement (i.e., that OT is getting to the brain and influencing social processes) and to establish optimal dosing of OT. Promising neurophysiological measures of target engagement for OT include EEG mu suppression while observing biological motion, and pupillary dilation during an emotion recognition task.

The R21 phase will determine the dose-response curve to OT for proposed measures of target engagement (i.e., mu suppression and pupillary dilation). The proposed study will use a single administration, within-subjects, crossover design to model the dose-response to OT across a large range of doses. Subjects with schizophrenia will be randomized to either: 8, 12, 24, 36, 48, 60, 72, or 84 IU OT (6 subjects to each dose). Each subject will receive OT and placebo in administrations separated by one week in randomized order. 30 minutes following OT administration, mu suppression and pupillary response will be assessed. We will also collect data on two measures of social salience (operationally defined here as behavioral tasks of social preference) to examine their correlations with measure of target engagement.

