The inability to use peripheral blood to estimate brain levels of OT has been an important impediment for clinical research with OT. As a result, important decisions for clinical trials, including dose and duration of drug action, have been based on very limited information. This is a substantial problem since studies in animals indicate that the dose-response of OT differs for different behavioral effects with some showing inverted-U shaped dose responses[20]. In addition, it has been difficult to explain why some individuals respond to OT and others do not. The R21 phase of this proposal will evaluate promising indicators of OT's effects on the brain, specifically examining the dose-response relationship for our proposed psychophysiological target measures of neural engagement. If these responses are reliable and valid indicators of OT's brain activity, they have the potential for facilitating treatment development by providing information for dosage selection, duration of drug effects, and identification of non-responders. This proposal will not be able to link OT to a particular receptor – such an approach to target engagement will only be feasible when a PET ligand for the OT receptor is identified. However, our proposed approach can indicate that intranasally administered OT has entered the brain and engaged a social processing network.

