### **Potential Benefits:**

The R21 may result in a better understanding of the relationship between OT dose and the response of a brain network associated with social information processing. This could result in a more scientific approach to making decisions about the dose of intranasal OT.

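### C.1.h says the dose range guarantees a stable optimal-dose estimate, but it gives that dose no usable definition and no precision, and six subjects per dose do not guarantee one

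*Combined protocol and SAP*

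**What the plan says.** C.1.h (Data Analysis) fits a 4-parameter logistic curve, with a 5-parameter version as a check. It tests whether the upper asymptote differs from zero "using a z-test based on the parameter estimate and its standard error". This is described as a test for a change "at the optimum dose of OT (where the upper asymptote is reached"). No percentage of maximum and no other numeric rule turns that description into a dose. The only standard error mentioned is the one for the asymptote.

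The Power paragraph simulates 8 doses with 6 observations each and reports results for the asymptote test only. It begins "Under these assumptions the power for detecting a significant upper asymptote is 84% for pupillary response data" at d = .81, then gives 92% at d = 1.22, 89% at d = 1.03 and 45% at d = .24. It closes with the claim that "our design ensures that we will be able to find a stable estimate for the optimal dose of OT".

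Dose is a stated purpose of this phase. The protocol introduction includes in the R21 step "to establish optimal dosing of OT". Section A.3 presents the measures as "providing information for dosage selection, duration of drug effects, and identification of non-responders". Potential Benefits adds: "This could result in a more scientific approach to making decisions about the dose of intranasal OT".

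**The concern.** Showing that a plateau exists and showing at which dose it begins are different tasks. The first pools information from every dose on the plateau. The second depends on the shoulder of the curve, where neighbouring doses differ little. Good power for the first says nothing direct about precision for the second, yet the plan asserts the second without reporting a result for it.

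What is at stake is the dose conclusion of the R21. With no rule for the optimum and no planned interval, one dose could be named after the data are seen although the data are compatible with an optimum at several other tested doses. That would weaken the contribution the protocol promises on dosing.

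**Working it through.** **Inputs from the plan.** Doses 8, 12, 24, 36, 48, 60, 72 and 84 IU; 6 subjects each (n = 48). Upper asymptote equal to d. Full variance at 24 to 60 IU and half at the four extreme doses (the Power paragraph lists 74 IU where the design has 72; 72 is used here). **Not given:** E50, slope, alpha, sidedness, handling of failed fits.

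**1. The plan's powers.** They cannot be derived from the stated inputs alone. With a fixed standard error and a two-sided 5% test (assumed), SE = d / (1.960 + z of the power):

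- d = .81, 84%: .81 / (1.960 + 0.994) = 0.274
- d = 1.22, 92%: 1.22 / (1.960 + 1.405) = 0.363
- d = 1.03, 89%: 1.03 / (1.960 + 1.227) = 0.323
- d = .24, 45%: .24 / (1.960 − 0.126) = 0.131

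No single SE gives all four, but a simulated nonlinear fit can come close. A 4-parameter logistic in dose, with E50 24 IU, slope .06 per IU, weighted fit, one-sided 5% test and converged fits only, gives 42 / 83 / 89 / 91% at d = .24 / .81 / 1.03 / 1.22. The stated values are 45 / 84 / 89 / 92%.

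**2. The optimum as defined.** For f(x) = L + (U − L) / (1 + exp(−b(x − E50))), f(x) = U needs exp(−b(x − E50)) = 0, which no finite x satisfies. A cut-off is needed, and it matters. With E50 = 24 and b = .06:

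- ED80 = 24 + ln 4/.06 = 47 IU
- ED90 = 24 + ln 9/.06 = 61 IU
- ED95 = 24 + ln 19/.06 = 73 IU
- ED99 = 24 + ln 99/.06 = 101 IU, beyond the tested range

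**3. Hand check of precision.** In change-SD units (an assumption about d), the mean at a middle dose has SE 1/√6 = 0.41. At d = .81, with lower asymptote 0, the rise from ED50 to ED90 is 0.4 × .81 = 0.32, and from ED90 to the plateau 0.1 × .81 = 0.08. Both are smaller than the SE of one dose mean. Curve fitting pools across doses, so this indicates difficulty and does not prove it.

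**4. Simulated intervals for ED90.** Three separate sets of assumptions were run.

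*Set A, matched to the plan's powers.* Of 7056 settings (curve, fit, weighting, scale of d, sidedness, handling of failed fits), 46 recovered all four powers, with a largest miss of 4.3 points in a fresh run. Of the 46, 22 use the planned 4-parameter fit. Among trials passing the asymptote test, ranges over settings (median setting in brackets) were:

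| d | tested doses inside the median 95% profile interval | trials with upper limit above 84 IU |
|---|---|---|
| .24 | 6–8 (8) | 96–100% (99) |
| .81 | 4–8 (6) | 69–94% (86) |
| 1.03 | 4–8 (6) | 55–87% (76) |
| 1.22 | 3–7 (5) | 45–80% (69) |

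At d = .81 the 4-parameter settings alone also give 4–8 (6), as does replacing ED90 by ED80 or ED95. Excluding shallow slopes leaves 4–8 (6), but the share above 84 IU becomes 14–93% (81). The intervals contain the true ED90 in 94–99% of passing trials.

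*Set B, different code and settings.* Of 672 combinations, 29 matched all four powers within 4.2 points. At d = .81 the median profile interval covered 5 to 8 of 8 doses, and always 8 when the lower asymptote was free.

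*Set C, not matched to the powers.* Eight assumed curves, lower asymptote free or fixed at 0: 5–8 of 8 doses at d = .81 and 4–8 at d = 1.22, with the upper limit above 84 IU in 70–100% of trials.

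**5. Smallest stated effect.** At d = .24 the plan's own power is 45%. In 100 − 45 = 55% of such trials the mu-suppression data would not establish a non-zero plateau, and so would give no basis for locating where it starts.

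**The case against.** **The sentence carries little weight.** The calculations are framed around detecting engagement; H1, H2 and the Go/No Go rule in C.1.i rest on that test and not on the dose. The R33 needs a new IRB submission (Duration of Research), where a dose rule could be set. This stands, and it limits the consequence to what the R21 can say about dose. It does not supply a result for the stated property.

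**The counts are reverse-engineered.** This stands. Set A kept 46 of 7056 settings, and 24 of those fix the lower asymptote at zero, which is not the planned model. In Set B, 26 of 29 matches needed a one-sided test with only converged fits counted. The two sets differ for the planned model (4–8 against always 8), so the count depends on implementation. It is an illustration. Set C does not rely on matching and points the same way.

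**Stable could mean little scatter in the point estimate.** That is a fair reading, and Set A is kinder on it: at d = .81 the middle 80% of estimates is 20–42 IU wide (median 30), or 1–3 tested doses. In Set B the 10th-to-90th percentile widths run from 27 IU (9 to 36) to 84 IU (17 to 101). Against a tested range of 84 − 8 = 76 IU, neither set supports a guarantee.

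**Many doses on a plateau are nearly equivalent.** Also right. On the curve in step 2, with lower asymptote 0, 48, 60, 72 and 84 IU give about 81, 90, 95 and 97% of the plateau. A reader might therefore infer that doses inside an ED90 interval are indistinguishable and doses outside it are shown to differ. That does not follow: doses above the upper limit lie on the same plateau, and the interval does not compare responses between doses.

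**True effects may be larger.** The plan calls its assumptions conservative. Precision does improve at d = 1.22, but not to the point of a guarantee.

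**Conclusion.** The point holds as an overstated and undefined property. C.1.h defines the optimum by a level that its own model does not reach at a finite dose, and it reports no precision for that dose. Under a wide range of assumed curves with 6 subjects per dose, the typical 95% interval for ED90 at d = .81 covers about half or more of the tested doses and usually passes 84 IU. At d = .24 even detecting a plateau has 45% power. The design does not ensure a stable optimal dose.

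The size rests on assumed E50, slope, alpha and sidedness, on ED90 as the definition, and on a monotone curve, although A.3 itself mentions inverted-U responses in animals. Several different settings fit the four powers, so the plan's own settings are not identified.

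Three stronger readings are tempting and not supported. The stated powers are not shown to be wrong, because inputs needed to reproduce them are missing. It cannot be said that the dose estimate was never simulated, only that no result is reported. The Go/No Go decision is not undermined, because it does not use the dose.

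**What to change.** In the Power paragraph, delete the guarantee and replace it with a definition and a result, for example: *The optimal dose is defined as the ED90 of the fitted curve. In the simulations above, assuming E50 = [ ] and slope = [ ], its median 95% interval was [ ]–[ ] IU at d = .24, [ ]–[ ] at .81, [ ]–[ ] at 1.03 and [ ]–[ ] at 1.22.* An alternative definition is the lowest tested dose whose fitted response is at least 90% of the fitted upper asymptote. Either way, state whether the 90% refers to the upper asymptote or to the rise from the lower one, since these coincide only when the lower asymptote is zero.

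Add to C.1.h: *The optimal dose will be reported with a profile-likelihood or bootstrap 95% interval. If the upper limit exceeds 84 IU, the optimum will be reported as not bounded by the tested range. No single dose will be named as the established optimum when the interval spans several tested doses.*

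The cost is wording, one more output from a simulation already run and one interval in the analysis. The downside is a less favourable claim. Sample size, doses and the Go rule do not change. If the plan's own simulation yields a tight interval, reporting it would support a claim of stability under the stated assumptions.
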